6.6 Missed OIT (Investigational Product) Doses during Up-dosing

Missed doses of IP at any phase of the study can pose a significant risk to subjects, but the risk is believed to be highest during the Up-dosing Period. The algorithm for missed consecutive doses of IP is as follows:

- Miss 1 to 2 doses in a row – The next dose would be at the current dose level and could be given at home

- Miss 3 to 4 doses in a row – The next dose would be the current dose and would be given under supervision in the CRC
- Miss 5 to 7 doses in a row – Initiate the next dose at approximately 50% of the last tolerated dose (to the nearest feasible available whole dose listed in [Table 2](#) that is \leq 50% of the last tolerated dose). Dosing below 3 mg/day is not allowed. This dose is to be administered under supervision in the CRC. If tolerated, dose escalation may resume with dose increases of 1 dose level occurring no more frequently than weekly and generally no less frequently than every 4 weeks until the subject has returned to the dose level at which the lapse in dosing occurred. If symptoms occur, the dosing guidelines for the up-dosing period apply.
- Missing > 7 consecutive days of dosing due to non-compliance (ie, for any reason other than treatment of an AE or an IP dispensing error) constitutes an individual stopping rule and the subject is to stop taking IP. The subject will be considered an escalation failure non-responder, and will be asked to return to the CRC 14 days following their last dose of IP to undergo an Early Discontinuation Visit ([Section 6.3.6](#)).
- Additionally, excessive missed dosing, defined as 3 consecutive days of missed doses on 3 or more occasions during the Up-dosing Period, for any reason other than treatment of an AE, constitutes an individual stopping rule and the subject is to stop, constitutes an individual stopping rule and the subject is to stop taking IP. The subject will be considered an escalation failure non-responder, and will be asked to return to the CRC 14 days following their last dose of IP to undergo an Early Discontinuation Visit ([Section 6.3.6](#)).
- Temporarily withholding IP dosing – this may be instituted as treatment for an inter-current AE or to aid the Investigator in determining if a dose level is or is not tolerated, but the duration of withholding IP may not exceed 14 consecutive days, or the subject will be discontinued from the study. The manner in which dosing may resume after withholding dosing of IP depends on the duration for which dosing was withheld.
- If IP has been withheld for 8 to 14 consecutive days as treatment for an AE or due to an IP dispensing error, dosing may be reinitiated at approximately 25% of the last tolerated dose (to the nearest feasible available whole dose listed in [Table 2](#) that is \leq 25% of the last tolerated dose). Dosing below 3 mg/day is not allowed. The reduced dose is to be administered under supervision in the CRC. If tolerated, dose escalation may resume with dose increases of 1 dose level occurring no more frequently than weekly and no less frequently than every 4 weeks until the subject has returned to the dose level at which the lapse in dosing occurred. If symptoms occur, the dosing guidelines for the Up-dosing period apply.
- If IP has been withheld for ≥ 15 consecutive days for any reason, at any point in the study (with the exception of a dosing hiatus instituted for chronic/recurrent GI AEs at or before the 20 mg dose level, as per [Section 6.5.3.2](#)), the subject will be considered an escalation failure non-responder, and will be asked to return to the CRC 14 days following their last dose of IP to undergo an Early Discontinuation Visit ([Section 6.3.6](#)).

No attempt should be made to make up for a missed dose if greater than 6 hours have elapsed since usual time of dosing.

6.7 Skin Prick Test

Subjects will have SPTs performed using routine clinical procedures for food allergens (perennial allergens and seasonal allergens at screening only). After the subject is off antihistamines for an appropriate length of time (5 half-lives of the antihistamine that is being used), a skin test probe is pressed through a commercial extract of an allergen into the epidermis. Positive (histamine) and negative (saline-glycerin) controls are placed to establish that the response is not blocked and to determine if there is dermatographism, respectively.

6.8 Visit Windows

Strict adherence to the dosing schedule should be maintained:

- Study visits should occur within a \pm 2-day window of the scheduled visit date (ie, 2 days before or 2 days after the scheduled visit date)
- The Early Discontinuation Visit is to occur 14 days after the last dose of IP where IP dosing has been ceased for reasons other than study completion. The permissible window is minus 3 days to plus 7 days.

7. SAFETY MONITORING

This section defines the types of safety events that should be reported and outlines the procedures for appropriately collecting, grading, recording, and reporting them. A DSMC will be established to monitor study safety events and will meet approximately quarterly throughout the study.

7.1 Reporting of Safety Events

All safety events observed under this protocol are to be reported through the electronic data capture (EDC) system for the duration of the study. Some safety events arising under certain defined conditions are recorded on specific forms as follows:

- Any allergic symptoms observed during in-clinic dosing will be recorded directly on the Escalation/In-Clinic Dosing form (also referred to as an IP Administration form), and are not to be recorded on an AE form (to avoid duplicate reporting) unless the event is considered an SAE. These symptoms are, however, by definition, AEs (Section 7.2) and will be reported as such in the database.
- If any safety event meets the definition of an SAE (whether or not related to dosing), it will also be recorded on an AE/SAE form.
- Non-serious adverse events of interest (AEIs) are reported on a non-serious AEI form and include anaphylaxis episodes meeting the criteria below, accidental food allergen exposures, GI AEs resulting in prolonged disruption of dosing, AEs associated with the use of epinephrine, and severe AEs (Section 7.3.4). These events will be reported to ProPharma Group following the same process as SAE reporting (with the exception of the requirement for regulatory submission). Only one form will be used per episode (eg, a systemic allergic reaction that meets anaphylaxis criteria in the protocol, involves

at least one severe symptom, and requires epinephrine use will be reported once, on either an SAE or non-serious AEI report form).

7.2 Dosing Symptoms as Adverse Events

Although signs and symptoms of allergic reaction, especially those that are mild in severity, are frequent and expected occurrences in response to dose escalation during OIT, they still constitute AEs. As such, the start and stop times of dose-related allergic reactions, as well as any therapeutic interventions and relatedness to IP, will need to be recorded (Section 7.6.1).

It is common for allergic reactions, especially allergic reactions to food allergens, to manifest with multiple symptoms. When multiple symptoms are noted during the same episode, it is up to the Investigator to determine whether one, or more than one, AE has occurred. For allergic / hypersensitivity reactions involving multiple symptoms, each individual symptom is to be entered on a separate log line on the AE eCRF. For each symptom, the AE eCRF will query “Is this an allergic reaction?” and the site should indicate yes/no accordingly.

7.3 Definitions

7.3.1 Adverse Event

An AE is any untoward medical occurrence in humans, whether or not considered drug related, which occurs during the conduct of a clinical trial. Any change in clinical status, electrocardiograms, routine labs, x-rays, physical examinations, etc, that is considered clinically significant by the Investigator is considered an AE.

7.3.2 Adverse Reaction

A suspected adverse reaction is any AE for which there is a reasonable possibility that the drug caused the AE. A reasonable possibility implies that there is evidence that the drug caused the event.

Adverse reaction is any AE caused by the drug.

7.3.3 Serious Adverse Event

An SAE is an AE that results in any of the following outcomes:

- Death
- Life-threatening AE (Life-threatening means that the study subject was, in the opinion of the Investigator or Sponsor, at immediate risk of death from the reaction as it occurred.)
- Inpatient hospitalization or prolongation of existing hospitalization
- Persistent or significant incapacity or substantial disruption of the ability to conduct normal life functions
- Congenital abnormality or birth defect
- Important medical event that may not result in one of the above outcomes, but may jeopardize the health of the study subject or require medical or surgical intervention to prevent one of the outcomes listed in the above definition of an SAE.

It is anticipated that the most likely cause of SAEs in this study will be anaphylaxis; however, not all occurrences of anaphylaxis are necessarily SAEs. Guidance for determining when anaphylaxis should be reported as an SAE is provided in [Appendix 6](#).

7.3.4 Adverse Event of Interest

The safety profile of OIT is well established. The Phase 2 safety experience with AR101, as outlined in the Investigator Brochure, is generally consistent with this profile. Nonetheless, 5 types of AEs have particular importance in further assessment of the AR101 safety profile. These 5 types of AEs have been designated AEIs in ARC007: anaphylaxis events; GI AEs resulting in prolonged disruption of dosing; accidental food allergen exposure; AEs featuring a severe symptom; and AEs associated with the use of epinephrine. These events will be submitted to the pharmacovigilance team at ProPharma Group on a non-serious AEI form within 24 hours of site knowledge of the event. However, the Sponsor will not expedite reporting of AEIs to regulatory health authorities unless the event fulfills reportable criteria (Section [7.7.2](#)).

It is possible that the same event could involve some combination of AEIs (eg, epinephrine use, anaphylaxis, severe symptoms) and/or seriousness criteria. Should this occur, one report form should be used so as to not duplicate reporting. The AEI form completion guidelines will be provided to sites in the manual of procedures.

The AEIs are each discussed further below.

7.3.4.1 Anaphylaxis Event

An anaphylaxis event is an AE that meets the definition of anaphylaxis in the 2014 position paper by the European Academy of Allergy and Clinical Immunology (EAACI) Food Allergy and Anaphylaxis Guidelines Group (Muraro et al, 2014). Accordingly, anaphylaxis is defined as a severe, potentially life-threatening systemic hypersensitivity reaction, characterized by being rapid in onset with life-threatening airway, breathing, or circulatory problems that is usually, though not always, associated with skin and mucosal changes.

With respect to the inclusion of being potentially life-threatening in the definition of anaphylaxis and how that relates to the assessment of anaphylaxis as an SAE, reference is made to the 2012 US Food and Drug Administration (FDA) Guidance for Industry and Investigators, Safety Reporting Requirements for INDs and BA/BE Studies that states, “An adverse event or suspected adverse reaction is considered ‘life-threatening’ if, in the view of either the Investigator or Sponsor, its occurrence places the patient or subject at immediate risk of death. It does not include an adverse event or suspected adverse reaction that, had it occurred in a more severe form, might have caused death.” Thus, for the reporting of anaphylaxis as an SAE, the severity of the reaction, assessed according to the EAACI system for grading the severity of anaphylactic reactions (Muraro et al, 2007), is also to be taken into account. Guidelines for when anaphylaxis may fulfill the seriousness criterion as an important medical event are provided in [Appendix 4](#).

When the diagnosis of anaphylaxis is made, the basis for having suspected the diagnosis must be documented, using the criteria established by the Second Symposium on the Definition and

Management of Anaphylaxis (Sampson et al, 2006). These criteria were again affirmed in the recently published International consensus on (ICON) anaphylaxis (Simons et al., 2014).

7.3.4.2 Gastrointestinal AE Resulting in Prolonged Disruption of Dosing (GI AEIs)

Gastrointestinal AEs, typically chronic/recurrent GI AEs, that result in a prolonged disruption of dosing will be considered AEIs and will be assessed longitudinally according to the procedures described below. For the purpose of delineating these AEIs, prolonged disruption of dosing is defined as withholding IP for > 7 days. This will include 3 categories of subjects:

- Any subject whose dose is withheld for > 7 days due to GI AEs and resumes dosing at a reduced dose level
- Any subject who develops chronic/recurrent GI AEs at or before reaching the 20-mg dose level and resumes dosing after a 30-day dosing hiatus
- Any subject who permanently discontinues dosing who had experienced GI AEs (Section 4.3.1).

All subjects who fall into any of these 3 categories will be asked to fill out the PEESS v2.0 questionnaire (Franciosi et al, 2011), with the assistance of a parent/ guardian, as appropriate, every month for 6 months. However, it should be noted that the PEESS v2.0 was not designed to establish a diagnosis of EoE, and has not been validated for use in subjects with GI symptoms of other etiologies. Furthermore, the discriminant validity of the questionnaire has not been reported in either longitudinal natural history or interventional studies. For these reasons, the use of the PEESS v2.0 to monitor the clinical course of GI symptoms must be considered exploratory. Nevertheless, the PEESS v2.0 has shown good content and construct validity for all subjects (Franciosi et al, 2011; Martin et al, 2015), and so holds promise for being a valuable tool to follow the clinical course of EoE or an EoE-like immune-mediated GI syndrome. Thus, the PEESS v2.0, could reveal trends toward symptomatic improvement or worsening that might otherwise go undetected.

Subjects who discontinue dosing prematurely due to chronic/recurrent GI AEs will be asked to return to the clinic for evaluation monthly for \geq 6 months (if the subject is asymptomatic, telephone follow-up with the Investigator may substitute for in-clinic visit, at the Investigator's discretion). If chronic/recurrent GI AEs persist beyond 6 months, subjects are to be followed with monthly clinic visits (telephone follow-up with an Investigator may substitute for in-clinic visit, at the Investigator's discretion) until the symptoms have resolved or are assessed to have stabilized with optimal medical management.

If a subject with chronic/recurrent GI AEs has not experienced complete resolution of symptoms within 6 weeks of discontinuation of dosing with the IP, the subject should be referred to a (pediatric) gastroenterologist.

If a subject who discontinued dosing with the IP prematurely due to chronic/recurrent GI AEs is unable to discontinue the use of symptomatic therapies that may have been initiated to treat the GI AEs (eg, H1 or H2 histamine blockers or proton pump inhibitors) by 12 weeks from the time that IP was withdrawn, the subject should be referred to a (pediatric) gastroenterologist.

As is the case for any AE occurring during the study, so it is for chronic/recurrent GI AEs that the Investigator may, at any time, and at his or her discretion, request consultation from an outside physician or additional testing to assist in the diagnosis or management of the AE.

If a subject is seen by a gastroenterologist, the investigational site is to procure records of the visit, as well as any test results, including those from endoscopy and endoscopic biopsy, if performed. These are to be retained with the subject's source documentation.

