4.3 Early Termination

4.3.1 Criteria for Early Termination

Any subject will be prematurely terminated from additional IP exposure for the following reasons:

1. Life-threatening symptoms (Consortium of Food Allergy Research [CoFAR] Grade 4; refer to the table in [Appendix 5](#)), including, but not limited to, anaphylaxis resulting in hypotension, neurological compromise, or mechanical ventilation secondary to peanut OIT dosing or any peanut food challenge
2. Severe symptoms (CoFAR Grade 3; refer to the table in [Appendix 5](#)), including, but not limited to, those that require intensive therapy (to be determined by the Investigator, but may include such interventions as intravenous (IV) epinephrine, intubation, or admission to an intensive care unit) or those that are recurrent

Any subject may be prematurely terminated from additional IP exposures for the following reasons:

1. Poor control or persistent activation of secondary atopic disease (eg, atopic dermatitis, asthma)
2. Starting any prohibited medication (Section [5.10](#)), with no alternative medications available per the prescribing doctor, unless a waiver has been obtained from the Medical Monitor, as per Section [5.7](#)
3. Pregnancy
4. Non-adherence (non-compliance) with IP dosing, as indicated by missing > 7 consecutive dosing days on any 1 occasion, or 3 consecutive dosing days on 3 or more occasions during the Up-dosing Period, as this could constitute a potential safety issue
5. Medically-indicated circumstances (eg, as part of the treatment for inter-current AEs) that require missed IP dosing for > 14 consecutive days, with the exception of the voluntary 30-day hiatus for GI-related AEs occurring at or before the 20-mg dose level

Any subject may also be prematurely discontinued from the study if:

1. The subject elects to withdraw consent from all future study activities, including follow-up.
2. The subject is lost to follow-up (ie, no further follow-up is possible because attempts to reestablish contact with the subject have failed).
3. The subject develops biopsy-documented EoE.
4. The subject's continued participation in the study is assessed by the Investigator to constitute a threat to the safety of the subject or the safe conduct of the study.
5. The subject dies.
6. The Sponsor discontinues the study.

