6.5.3.2 Assessment of Chronic/Recurrent Symptoms

Gastrointestinal symptoms were the most common potentially allergic symptoms to occur on a subacute, chronic, and/or recurrent basis during Phase 2 clinical trials with AR101. Atopic dermatitis, seasonal allergies, or asthma are other potentially non-acute allergic reactions that could be brought on or exacerbated by OIT. The absence of a clear temporal relationship between dosing and the emergence of recurrent symptoms may help to distinguish these from acute dosing-related symptoms.

If symptoms arise that suggest a chronic/recurrent reaction to IP, the dose level should be reduced. As with acute symptoms, the level of the dose reduction should be guided by the severity of the symptoms. Symptomatic treatment is permitted (Section 6.5.6), but should be used as a supplement to dose reduction, not a substitute for it.

For chronic/recurrent GI symptoms, especially upper GI symptoms, Investigators are advised to have a low threshold for instituting a dose reduction and/or for considering early discontinuation of affected subjects from the study, owing to the potential for EoE.

For subjects determined to be having dose-limiting chronic/recurrent GI symptoms during up-dosing, at up to and including the 20 mg/d dose level, it is advised that dosing of IP be suspended for 4 weeks and resumed at a dose level of 3 mg/d for a minimum of 4 weeks, with the first dose given in the CRC under medical supervision. If tolerated, up-dosing may resume, with caution, according to the usual schedule, as tolerated. (Note: The 4-week suspension of dosing in response to chronic/recurrent GI symptoms occurring up to and including the 20 mg/d level is the only protocol-specified exception to the rules for missed OIT delineated in Section 6.6).

For subjects who develop dose-limiting chronic/recurrent GI symptoms at the 40 mg/d dose level or above, dose reduction and re-escalation is to proceed as described in Section 6.5.5.

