- Return to the CRC for dosing of a previously tolerated dose level, either a 1- or 2-step reduction (per Investigator judgment, based on severity of reaction). Dosing must be at a dose level listed in [Table 2](#).
- Institute the 4-week hiatus from dosing, with resumption of dosing at the 3 mg/d dose level, as permitted for recurrent GI symptoms occurring at or before the 20 mg dose level
- Discontinuation of dosing, with subsequent completion of an Early Discontinuation Visit

Any subject who discontinues up-dosing due to severe or repeated allergic reactions to IP should have their blood drawn for the assessment of peanut-specific immunoglobulin and CBC at, or as nearly as possible to, the time of the last dose but no later than at their Early Discontinuation Visit (Section [6.3.6](#)). Additional assessments are to be performed per Early Discontinuation Visit schedule.

Figure 2: Schematic for Up-dosing Period Dose Adjustment

Dose Adjustment in Response to Adverse Events

At the Investigator discretion, temporary dose reductions ranging from a 1-step decrement (ie, to the previous dose) to approximately half of the current dose level (to the nearest feasible available whole dose listed in [Table 2](#)) can be instituted as part of the treatment regimen for an inter-current AE. Dosing below 3 mg/day is not allowed. Also, if a pattern of decreased tolerability of IP during menses is discerned, then a temporary dose reduction can be instituted during this time. Temporary dose reductions for inter-current AEs may be instituted as follows:

- For dose reductions of \leq 4 consecutive days, whether dose re-escalation is to occur at home or in the CRC is at the Investigator's discretion. If the reduction in dose is maintained for \leq 4 consecutive days, then the pre-reduction dose level may be resumed, with the biweekly escalation schedule kept unaltered.
- If a reduction in dose is maintained for 5 to 7 consecutive days, then the subject is to return to the CRC to undergo dosing under medical supervision. At the Investigator's discretion, the pre-reduction dose level may be resumed or dosing may continue at the reduced dose level. The biweekly escalation should be reset so that the subject receives \geq 2 consecutive weeks of treatment at the dose level assigned (either the reduced or the pre-reduction dose level).

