7.9.2 Individual Stopping Rules

Individuals may stop the study at any time by withdrawing their consent if they experience subjectively intolerable AEs, dosing symptoms, or for any other reason. In addition, > 7 consecutive days of missed daily dosing due to non-compliance (ie, for any reason other than treatment of an AE or an IP dispensing error) constitutes an individual stopping rule. During Up-dosing, subjects must halt up-dosing and re-start with a reduced dose if more than 4 days of dosing are missed. Missing 3 or more consecutive days on 3 occasions is an individual stopping rule, as is missing 15 or more consecutive days of dosing for any reason, with one exception of the voluntary 4-week hiatus for GI AEIs occurring at or before the 20 mg dose, as specified in Section 6.5.3.2.

Occurrence of any of the following will result in the cessation of dosing and the subject being discontinued from the study as an escalation failure non-responder, resulting in an Early Discontinuation Visit within 14 days:

- Failure to accomplish up-dosing of IP after 3 attempts
- Failure to identify a tolerated dose of IP after 3 attempts at dose reduction

Finally, administration of 3 or more doses of epinephrine for the treatment of any dose-related allergic reaction in any subject is an individual stopping rule.

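### The GI dosing hiatus has two lengths (4 weeks and 30 days), and a child at 3 mg held 8 to 14 days for GI events meets the protocol's definition of prolonged disruption but no category that triggers PEESS

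*Protocol*

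**What the plan says.** **Length of the hiatus.** The protocol allows one pause in dosing for GI events at or below the 20 mg level.

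- Section 6.5.3.2: "it is advised that dosing of IP be suspended for 4 weeks and resumed at a dose level of 3 mg/d".
- Section 6.5.5.2, among the options for reactions at home: "Institute the 4-week hiatus from dosing, with resumption of dosing at the 3 mg/d dose level".
- Section 7.9.2 exempts from the rule on 15 or more missed days a "voluntary 4-week hiatus for GI AEIs occurring at or before the 20 mg dose".
- Section 4.3.1 sets out when a subject may be terminated for more than 14 consecutive missed days, "with the exception of the voluntary 30-day hiatus for GI-related AEs occurring at or before the 20-mg dose level".
- Section 7.3.4.2, category 2: "Any subject who develops chronic/recurrent GI AEs at or before reaching the 20-mg dose level and resumes dosing after a 30-day dosing hiatus". Appendix 1 footnote o and Appendix 7 repeat the 30 days.

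**The GI AEI categories.** Section 7.3.4.2 first defines prolonged disruption as IP withheld for more than 7 days, with no condition on the restart dose. It then lists three categories. Category 1 is: "Any subject whose dose is withheld for > 7 days due to GI AEs and resumes dosing at a reduced dose level". Category 2 is the hiatus. Category 3 is permanent discontinuation in a subject who had GI events. Monthly PEESS for six months is tied to membership of one of the three.

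**The dose floor.** Sections 3.3, 6.5.5 and 6.6 do not allow dosing below 3 mg/day.

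**The concern.** The hiatus is the one protocol-specified exception to the missed-dose rules. With two lengths in the text, sites can differ on when a child has used up the exception and on when category 2 is met.

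The category list is also narrower than the definition above it. Category 1 requires a dose reduction, which cannot happen at the floor. At stake is the prescribed PEESS follow-up of some children with GI events at the first up-dosing level. Section 6.5.3.2 advises a low threshold for acting on chronic or recurrent GI symptoms because of possible EoE, so a gap in follow-up there is unwelcome even if few children fall into it.

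**Working it through.** The plan gives no figure to reproduce. The check is a unit conversion followed by a case-by-case test of the categories.

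**Step 1, units.** 4 weeks × 7 = 28 days; 30 − 28 = 2 days' difference.

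**Step 2, restart doses.** After a hold of 8 to 14 days for an adverse event, section 6.6 restarts at the nearest Table 2 level not above 25% of the last tolerated dose, with a floor of 3 mg:

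- 3 mg: 0.25 × 3 = 0.75, so 3 mg by the floor
- 6 mg: 0.25 × 6 = 1.5, so 3 mg by the floor
- 12 mg: 0.25 × 12 = 3, so 3 mg
- 20 mg: 0.25 × 20 = 5, so 3 mg
- 40 mg: 0.25 × 40 = 10, so 6 mg

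After the hiatus, which applies up to 20 mg, sections 6.5.3.2 and 6.5.5.2 restart at 3 mg.

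**Step 3, test each case.** Category 1 needs a hold of more than 7 days and a restart below the previous level. Category 2 is tested twice: with 30 days taken literally, and with 4 weeks and 30 days taken as the same pause.

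| Level when held | Hold (days) | Restart | Cat. 1 | Cat. 2, literal | Cat. 2, same pause | In a PEESS category? |
|---|---|---|---|---|---|---|
| 3 mg | 8–14 | 3 mg | no | no | no | **no, on either reading** |
| 3 mg | 28–29 | 3 mg | no | no | yes | only if same pause |
| 3 mg | 30 | 3 mg | no | yes | yes | yes |
| 6, 12, 20 mg | 8–14 | 3 mg | yes | no | no | yes |
| 6, 12, 20 mg | 28–29 | 3 mg | yes | no | yes | yes |
| 6, 12, 20 mg | 30 | 3 mg | yes | yes | yes | yes |
| 40 mg | 8–14 | 6 mg | yes | no | no | yes |

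Above 40 mg the 25% rule always gives a lower level, so category 1 applies. Holds of 7 days or less do not meet the definition. Holds of 15 days or more outside the hiatus end dosing under section 6.6, which leads to category 3.

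**Step 4, the missed-dose exception.** Section 7.9.2 words it as 4 weeks and section 4.3.1 as 30 days. Section 6.6 states no length of its own and refers to 6.5.3.2. A child returning after 29 or 30 days is inside one wording and beyond the other.

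**The case against.** A reader might infer that any child held at 3 mg fits no category that allows resumption and so escapes PEESS. The documents do not support that. Category 2 has no dose-reduction condition and covers events at any level up to 20 mg. Section 6.5.3.2 calls its 4-week suspension the only exception to the missed-dose rules, so the two lengths most naturally describe one pause. On that reading a child who takes the hiatus at 3 mg is in category 2, and at 30 days or more the child is there on any reading.

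A reader might also infer that 24-hour reporting is lost. Section 7.3.4 ties that report to GI events with prolonged disruption, and the definition in 7.3.4.2 is met by a hold of more than 7 days alone. Nor is sub-study case status clearly lost: the Appendix 7 design text defines cases by withdrawal or protracted disruption, although its case definition repeats the three categories.

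On the missed-dose exception, section 6.8 allows visits within 2 days either side. If that window applies to the return visit, 28 ± 2 gives days 26 to 30, which absorbs the difference. No passage links the window to the hiatus, however. The section 4.3.1 entry is permissive, and the suspension itself is only advised.

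Other wording softens the PEESS gap without closing it. The synopsis lists PEESS for GI events that interrupt dosing, which is broader and adds a second trigger. Section 6.4 permits PEESS at unscheduled visits but does not require it.

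Finally, a reader might size the problem by noting that 3 mg is one of four levels at which the hiatus applies. The documents do not say how GI holds are distributed over levels, and most kinds of hold at 3 mg are covered, so that count gives no share of children affected.

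**Conclusion.** Two inconsistencies stand. The hiatus has two lengths, 28 and 30 days, in current text. The category list in 7.3.4.2 omits some subjects who meet the section's own definition: those at 3 mg held 8 to 14 days for GI events who resume at 3 mg. A 28- or 29-day hiatus at 3 mg is also missed, but only if 30 days is read literally.

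The effect is small. It is confined to the lowest up-dosing level, and it concerns PEESS follow-up and consistent site conduct. The protocol calls this use of PEESS exploratory, and SAP 9.8.13 describes it only for subjects who discontinue, so no planned analysis is shown to change. The result assumes restart doses as set out in sections 6.6, 6.5.3.2 and 6.5.5.2. This is a minor point, worth correcting because a stated follow-up rule leaves out children whom the section's definition includes.

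**What to change.** 1. Reconcile the hiatus to one length in sections 4.3.1, 6.5.3.2, 6.5.5.2, 7.3.4.2 and 7.9.2, Appendix 1 footnote o and Appendix 7. Which length is for the sponsor to decide. State whether the section 6.8 visit window applies to the return visit.
2. Align the category list in 7.3.4.2, Appendix 1 footnote o and Appendix 7 with the section's own definition of more than 7 days withheld, so that subjects who resume without a dose reduction are included. Bring the synopsis wording of the PEESS trigger into line.

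The cost is a protocol clarification and a few more PEESS forms.
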